Scheme. Participants will be randomly assigned to group (1:1) using a computer-generated program overseen by [name]. The randomization scheme will be stratified by site (D-H and UAB), time since treatment completion (i.e., <6 months and >6 months), and receipt of chemotherapy (yes versus no) and will be blocked within strata (block lengths of 2 and 4 varied randomly).

Process and blinding. The PI or project managers will manage the randomization process, looking up the id number in an established excel file and assigning the local interventionist to communicate assignment to the participant and initiate treatment activities. The project coordinators will remain blind to group assignment and participants will be instructed not to discuss their assignment with the project coordinator collecting the outcome assessments.

When and How to Withdraw Subjects

Participants will be withdrawn from the study at their request (e.g., lack of interest in or perceived need for intervention, lack of time for study assessments).

Data Collection and Follow-up for Withdrawn Subjects

Our team continues to attempt to contact participants for each session and study assessment unless and until they ask us to stop/express the desire to withdraw. Each study contact is an extension of informed consent where participants are told what is occurring, what happens next, and that their participation is voluntary. When we are unable to reach participants by telephone for at least 30 days we send a letter conveying our attempts to reach them and ask them to contact us to continue with study activities or withdraw, as they prefer.

Treatment Regimen

Theoretical Background of BA/PS

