Minimally important differences. The minimally important differences (MID) between the two study arms are taken to be 10% of the practical range of the outcome variable[31] and thus the MIDs are 3.94, 3.95 and 11.2 for satisfaction with participation, ability to participate, and quality of life, respectively. Note that these MIDs are not data dependent, although standard deviations might change for different data sets. We will assume the standard deviation for the two PROMIS scales are both 10 according to the scoring manual and the standard deviation for FACT-B is 24, as estimated from our third pilot study.[29]

Estimated attrition. To estimate attrition, we examined the attrition seen in our three preliminary studies. One of the preliminary studies was an RCT,[25] two studies used a single arm design,[29] and each of the studies had at least three assessments. On average, 80% of our participants completed all study activities, and thus we expect an attrition of ~20% (if 300 people enroll, at least 240 participants will complete the study).

Power. Using a Time-Averaged Difference approach,[81] at a corrected significance level of $.05/3=.017$, and with three time-points post baseline, the required sample size to test for the minimally important effects of BA/PS on participation (PROMIS scales) ranges from 63 to 117 in each arm to achieve 80% power for within subject correlations ranging from 0.2-0.8. The required sample size to test for the minimally important effect of BA/PS on quality of life (overall FACT-B score) ranges from 45 to 83 in each arm to achieve 80% power for within subject correlations ranging from 0.2-0.8. An FDR correction (see section C.7.3) will be used at the time of analysis which will provide more power than a Bonferroni correction and adequate control to the number of Type I errors.

Statistical Methods

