Data analysis will begin with descriptive statistics for baseline participant characteristics and outcomes by study group. We will calculate means, standard deviations, and percentiles for continuous variables (e.g., participation, quality of life, coping, goal adjustment, distress, age, etc.) and frequencies and proportions for categorical variables (e.g., clinical characteristics), at each time point as appropriate. We will plot and inspect the distributions of the outcome variables, and examine the validity of any extreme values (data entry errors will be minimized by logic checks in the Velos data collection system, and inspection of scheduled reports during data collection). We will examine balance between study groups with respect to baseline characteristics using effect sizes such as the standardized mean difference for numerical variables and Cramer's V for categorical variables. We will examine patterns of missing data due to dropout, and whether baseline characteristics are associated with dropout. Baseline factors showing non-trivial imbalances between groups or that are predictive of dropout, will be then used as adjusting covariates in the longitudinal group comparisons. We will use the latest versions of standard statistical packages (SAS and R) for all analyses.

Group Comparisons (Aim 1, Aim 2, and Exploratory Aim)

Objective. Our objective is to compare the two groups' functional recovery over time in terms of participation (PROMIS scales; Aim 1), productivity (Disability Days and WLQ; Aim 1), quality of life (FACT-B; Aim 2) and coping style, distress, and goal adjustment (Brief COPE, HADS, and GDGRS; Exploratory Aim). All measures are collected at conceptually relevant time points of enrollment (T1), completion of the most intensive part of the intervention (T2), completion of the full intervention (T3) and six months after treatment completion (T4). The methods described below will be conducted upon each outcome variable.

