Modeling. A longitudinal model fitted with linear mixed methods will be used for each outcome. Numerical outcomes with markedly non-normal distributions, if any, will be modeled with more appropriate error distributions than the default normal (e.g., lognormal or generalized beta distributions). The focus of inference will be the between-group difference in outcome trajectories over the study time points, modeled by a time by group interaction. A random effect for subject will be fitted to account for covariance among repeated measures on the same individuals. If necessary, we will conduct covariate adjustment for baseline factors unbalanced between the groups or predictive of dropout. Time will be modeled as a categorical variable, to avoid the strong assumption of linear trajectories, and therefore the single test for the interaction effect will be a multiple-degree of freedom test. Model-predicted outcome means (a.k.a. LS-Means) by group at each time point will be computed to facilitate interpretation. The overall treatment effect will be computed as the between-group difference in change from baseline (change from T1 averaged over T2 to T4) estimated with a linear contrast.

Handling of Missing Data

Mixed modeling techniques and covariate adjustment will reduce the impact of missing data, as the missingness is not assumed completely at random (MCAR) but conditionally (on the covariates) at random (i.e., MAR, a milder assumption).[82] Should dropout exceed the 20% allowed by the sample size (section C.7.5), non-parametric multiple imputation[83] will be employed to determine the robustness of the conclusions for the main analyses under the milder MAR assumption. Because missing data due to non-ignorable or non-random drop out (i.e., MNAR) does not depend on the observed data, it presents the most complex situation to handle. Because of the non-invasive, supportive nature of the BA/PS intervention, as well as the attention control condition, *a priori*, we do not expect to encounter non-random dropout (and therefore MNAR). However, we will examine the tracking system records and logs with regard to dropout, to determine the main reasons for dropout. If sufficient indication of an MNAR mechanism is found, sensitivity analyses under different assumptions for the missing data mechanism will be conducted, following the methodology described by Molenberghs and Kenward[84] in which the missing data mechanism needs to be modeled explicitly.

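### The three randomisation factors are not pre-specified in the outcome model; the effect on the reported SEs is small, and for the planned random-intercept model its direction is not established

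*Combined protocol and SAP*

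**What the plan says.** **Allocation** (section 6, Method for Assigning Subjects to Treatment Groups, Scheme). Allocation is 1:1. "The randomization scheme will be stratified by site (D-H and UAB), time since treatment completion" and receipt of chemotherapy, and the scheme "will be blocked within strata (block lengths of 2 and 4 varied randomly". Three two-level factors give 2 × 2 × 2 = 8 strata.

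**Covariates** (section 9, Statistical Methods). After descriptive summaries by arm, the rule is: "Baseline factors showing non-trivial imbalances between groups or that are predictive of dropout, will be then used as adjusting covariates". The Modeling paragraph repeats it conditionally: "If necessary, we will conduct covariate adjustment for baseline factors unbalanced between the groups or predictive of dropout". Neither place names a stratification factor, gives a cut-off for imbalance, or says whether a covariate interacts with time.

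**Model and target** (section 9, Modeling). The model has categorical time, group, time by group and a random subject effect. Inference centres on the interaction, where "the single test for the interaction effect will be a multiple-degree of freedom test". The overall effect is the "between-group difference in change from baseline (change from T1 averaged over T2 to T4) estimated with a linear contrast". T1 is therefore one of the modelled outcomes.

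**Missing data** (section 9, Handling of Missing Data). The argument is that "the missingness is not assumed completely at random (MCAR) but conditionally (on the covariates) at random", so it depends on which covariates are in the model.

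**Relevance of the factors.** Section 4 (Time since treatment) allows that the one-year window may add heterogeneity. Section 9 (Recursive partitioning) lists site as a candidate predictor of average change from baseline. Neither gives a strength, and neither concerns chemotherapy.

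**The concern.** Stratified blocked allocation makes the treatment estimate more precise when the strata are prognostic. An analysis that leaves the strata out keeps that precision in the estimate but does not credit it in the reported SE. The rule in section 9 works against the design here: it selects covariates for imbalance, and blocking removes imbalance in exactly these three factors. Unstratified characteristics can be picked up by chance instead.

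At stake are the width of the interval for the change contrast, the calibration of that contrast and of the 3-df interaction test, and the SEs of the exploratory group differences at T2, T3 and T4. There is also a question of form. Because T1 is an outcome, a covariate entered only as a main effect largely cancels from a change-from-T1 contrast, so an adjustment coded that way would do little.

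**Working it through.** **Inputs.** From section 9, Sample Size Determination: SD 10 ("We will assume the standard deviation for the two PROMIS scales are both 10 according to the scoring manual"), MID 3.94 for satisfaction, significance level 0.05/3 = 0.0167, correlation 0.2 to 0.8, 240 completers (120 per arm). Assumed: correlation 0.5, complete data unless stated, and R2, the share of variance explained by the strata, at 5/10/15/20%.

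**1. The plan's own figure.** n per arm = 2 × [SD × (2.394 + 0.842)/MID]² × (1 + 2ρ)/3.
- PROMIS satisfaction: 62.94 → 63 at ρ = 0.2 and 116.9 → 117 at ρ = 0.8, as stated.
- FACT-B (SD 24, MID 11.2): 44.87 → 45 and 83.33 → 84. The plan states 83, which follows if the level is rounded to 0.017 (82.95).

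The formula has no covariates, so this point does not change it.

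**2. Can a stratification factor be selected for imbalance?** In 8,000 simulated blocked allocations of 300 women, Cramer's V for a stratification factor never exceeded 0.05 (maximum 0.034). For one unstratified binary characteristic, P(V > c) = P(chi-square on 1 df > 300c²) = 39/8/3% at assumed cut-offs of 0.05/0.10/0.125.

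**3. Strata predict change; random intercept; no other persistent differences in change.**
- Residual variance is 100 × (1 − 0.5) = 50. The variance of average change is 50 × (1 + 1/3) = 66.7.
- True SE of the contrast = √(66.7 × 2/120) = 1.054, with or without the factors in the model.
- The model pools its residual over three within-woman contrasts, only one of which carries the strata effect. So reported/true SE, factors omitted, is f = √[1 + R2/(3(1 − R2))].
- Nominal 5% size: contrast 2 × [1 − Φ(1.96f)]; interaction P(chi-square on 3 df > 7.815f²).
- Power at 0.0167: contrast Φ(3.94/1.054 − 2.394f), which is 91.0% at f = 1; interaction from a noncentral chi-square with noncentrality 3.94²/1.111 = 13.97 and critical value 10.24f², which is 79.7% at f = 1.

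| R2 of change | SE too large by | Contrast size | Contrast power | 3-df size | 3-df power |
|---|---|---|---|---|---|
| 5% | 0.9% | 4.8% | 90.7% | 4.7% | 78.9% |
| 10% | 1.8% | 4.6% | 90.3% | 4.4% | 77.9% |
| 15% | 2.9% | 4.4% | 89.9% | 4.1% | 76.9% |
| 20% | 4.1% | 4.1% | 89.4% | 3.7% | 75.7% |

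At assumed factor prevalences of 50/50/60%, these R2 need each factor to shift change by b points, where b² × (0.25 + 0.25 + 0.24) = 66.7 × R2/(1 − R2). That gives b = 2.2/3.2/4.0/4.7, so the last row is best read as an upper bound.

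**4. Unstructured covariance.** The variance of change is estimated directly, so the ratio with factors omitted is 1/√(1 − R2): 2.6/5.4/8.5/11.8% too large.

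**5. Strata shift only the level.** With complete data the change contrast is unaffected. With 20% dropout its SE moves by 0.2-0.4% at R2 of 10-20%. The visit-wise differences have SEs too large by 1/√(1 − R2), again 2.6/5.4/8.5/11.8%.

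**6. Other persistent differences in change.** Let strata explain R2 = 10% of change variance and other sources a share H. Total change variance is T = 66.7/(1 − R2 − H). The true variance per woman is 66.7 + HT. The random-intercept model reports (50 + 0.25(R2 + H)T) × 4/3 with factors omitted and (50 + 0.25HT) × 4/3 with factor-by-time terms.
- H = 0: ratio 1.018 with factors omitted.
- H = 5%: 70.6 against 70.6, ratio 1.000 with factors omitted.
- H = 10%: true 75.0. Omitted: 72.2, ratio 0.981, size 5.4%. Included: 69.4, ratio 0.962, size 5.9%. A simulation of 8,000 trials gave 5.7% and 6.2%.

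**7. Form of adjustment** (300 women, covariate shifting change by 3 points). With complete data a main effect moves the contrast by 0.000, and covariate by time by 0.14 on average. With 20% dropout unrelated to the covariate: 0.016 and 0.150. If dropout depends on the covariate in one arm only, bias relative to covariate by time is −0.099 with no covariate and −0.064 with a main effect. If it depends in opposite directions by arm: −0.208 and −0.138. If alike in both arms: under 0.01. The largest is 0.208/3.94 = 5.3% of the MID.

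**The case against.** The strongest objection is about direction. The claim that the SE is too large holds for the random-intercept model only if women differ persistently in change through the strata alone. Section 9 (Recursive partitioning) itself lists race, income and age as candidate predictors of average change. Step 6 shows that a modest amount of such heterogeneity cancels or reverses the error, and that adding the factors under a random intercept then moves the test further from nominal. This stands, and it is why the fix must also address the covariance.

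Second, nothing excludes the factors: any baseline factor that predicts dropout may enter. A reader might infer that the plan leaves them out altogether; the text supports only that they are not pre-specified.

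Third, no passage shows that the factors are prognostic, so every R2 is an assumption. This also stands.

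Fourth, the 5% and 0.0167 levels are not the planned decision rule, which is a 10% false discovery rate (section 9, Adjustment for Multiple Inference). The sizes and powers above show scale only.

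Fifth, section 9 never says that covariates enter as main effects only. Step 7 therefore shows why the form should be stated, not that the plan has chosen a weak one.

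**Conclusion.** The point holds as a low-severity gap in specification. Three factors that define the randomisation are not committed to the model, and the rule that could admit them is nearly blind to them by design.

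Three stronger readings are tempting and not supported.
- That the SE is too large whenever the factors predict outcome. For the planned change-from-T1 contrast with complete data they must predict change; a level shift affects only the exploratory visit-wise differences.
- That the planned tests are conservative. Under a random intercept this needs the absence of other persistent differences in change, which the documents do not establish.
- That the estimate is biased, or the trial too small. Omitting the factors biases nothing, and the stated sample sizes reproduce without them.

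Under the stated assumptions the SE error is about 1-4% (random intercept, strata the only source of persistent differences in change) or 2.6-11.8% (unstructured). In the first case power at 0.0167 falls by at most 1.6 points for the contrast (91.0% to 89.4%) and 4.0 points for the 3-df test (79.7% to 75.7%), both at the upper-bound R2.

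**What to change.** State before analysis that every outcome model includes group, categorical time, group by time, the three stratification factors as randomised, and each factor's interaction with categorical time, whatever their observed balance. Fit it with an unstructured within-woman covariance, or with robust SEs, so that adding the factors does not push a random-intercept SE below its true value. Keep T1 as an outcome and keep the planned contrast, so that women with only T1 data stay in the analysis.

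Remove imbalance-triggered covariate selection from the primary model. Any dropout predictors that are kept should enter with time interactions, under a rule fixed before outcomes are examined by arm.

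The cost is SAP wording. The factors are already recorded for randomisation. The model gains 3 + 9 = 12 fixed-effect parameters, and an unstructured covariance over four visits has 10 parameters where a random intercept has 2, with 300 women. Section 10 places inferential analysis after data collection, which was still open at this version. If outcomes have since been examined by arm, the change should be reported as made after that.

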Assessments. Assessments will be administered via telephone by a D-H research assistant blind to group assignment. Participants will complete outcome assessments upon enrollment (T1) and at 8 weeks (T2), 20 weeks (T3) and 44 weeks (T4) later. The T2 assessment captures the short-term outcomes of the most intensive part of the intervention (i.e., after six weekly sessions). The T3 assessment will capture the short-term outcomes at the end of the full intervention. The T4 assessment explores the sustained effect of BA/PS (six months after BA/PS ends). Our decision to include the T4 assessment was influenced by a systematic review that indicated it often takes six months to see maximum effects of interventions targeting participation in adults with physical disabilities.[46] The study aim is to test whether the BA/PS intervention affects the “slope” of functional recovery over time. With the longitudinal data, we will also be able to explore the pace of improvement and whether the two groups differ at these clinically relevant time points.

[figure not shown]
4. Subject Selection

Inclusion Criteria with justification

1. Age of 18 years or older.
2. Experiencing reduced participation (i.e., a score of ≥ 10 on the modified Work and Social Adjustment Scale[47]).
3. Females diagnosed with Stage 1-3 breast cancer and within one year of completion of locoregional treatment and/or chemotherapy with curative intent and absence of disease recurrence.

Biological variables of age and gender. In our pilot studies, the intervention has been flexible enough to be used with various challenges that occur across the age range.[25, 29] This proposal’s focus upon female breast cancer survivors reflects our pilot research population and allows us to focus recruitment resources with a smaller, closely aligned number of providers. We have decided to focus on females with breast cancer because of the very low prevalence rate of breast cancer in males. Because the D-H and UAB sites see a mean of 3.8 males each year with breast cancer, we will not enroll enough males to allow us to draw sound conclusions that are generalizable to a male population.

Medical co-morbidities. We considered the advantages and disadvantages of excluding women who have medical co-morbidities that affect their daily activities. Cancer survivors report an average of five

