Adjustment for Multiple Inference

A False Discovery Rate (FDR) approach[85] will be utilized to adjust inferential results for multiple inferences on the same body of data, separately for the primary analyses and the exploratory analyses. The FDR is the expected proportion of true null differences among those that are declared “significant”. The FDR will be set at 10%. All research products will disclose the number of inferences conducted and whether outcomes were primary or exploratory. As shown above, the sample is well powered to detect relevant effect sizes on the primary outcomes, even after multiplicity adjustment.

Heterogeneity of Intervention Effects

Rationale. We have developed the intervention to be flexible and responsive to the needs of a diverse group of breast cancer survivors. However, our diverse sample will give us the opportunity to identify any unanticipated moderator effects. Therefore, we will explore whether there are subgroups of participants who benefited most and least during the study, as per the primary outcomes.

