Intent to treat. Our main analyses will utilize an intention-to-treat approach. As the BA/PS intervention is not part of standard practice, cross-over events are not expected to occur. All available data from all participants who undergo randomization will be included in the analyses according to the group assigned, regardless of any post-randomization protocol deviations.

10. Monitoring and Quality Assurance

Safety and Adverse Events

Definitions

Unanticipated Problems Involving Risk to Subjects or Others

Any incident, experience, or outcome that meets all of the following criteria:

- Unexpected in nature, severity, or frequency (i.e. not described in study-related documents such as the IRB-approved protocol or consent form, the investigators brochure, etc)
- Related or possibly related to participation in the research (i.e. possibly related means there is a reasonable possibility that the incident experience, or outcome may have been caused by the procedures involved in the research)
- Suggests that the research places subjects or others at greater risk of harm (including physical, psychological, economic, or social harm).

Adverse Event

An **adverse event** (AE) is any symptom, sign, illness or experience that develops or worsens in severity during the course of the study. Intercurrent illnesses or injuries should be regarded as adverse events.

Abnormal results of diagnostic procedures are considered to be adverse events if the abnormality:

- results in study withdrawal
- is associated with a serious adverse event
- is associated with clinical signs or symptoms
- leads to additional treatment or to further diagnostic tests
- is considered by the investigator to be of clinical significance

Serious Adverse Event

Adverse events are classified as serious or non-serious. A **serious adverse event** is any AE that is:

- fatal
- life-threatening
- requires or prolongs hospital stay
- results in persistent or significant disability or incapacity
- a congenital anomaly or birth defect

- an important medical event

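### The stated power is for a one-degree-of-freedom post-baseline average; the group-by-time interaction named as the focus of inference was never sized

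*Combined protocol and SAP*

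**What the plan says.** **Power (section 9, Sample Size Determination).** The method is a time-averaged difference over three post-baseline visits, at .05/3. For the PROMIS scales the required number "ranges from 63 to 117 in each arm to achieve 80% power for within subject correlations ranging from 0.2-0.8". The differences to detect are 3.94 (satisfaction), 3.95 (ability) and 11.2 (quality of life), with SDs of 10, 10 and 24. Of 300 enrolled, 240 are expected to complete, or 120 per arm.

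**Analysis (section 9, Modeling).** The focus is the group-by-time interaction: "The focus of inference will be the between-group difference in outcome trajectories over the study time points, modeled by a time by group interaction". Time is categorical, and "therefore the single test for the interaction effect will be a multiple-degree of freedom test". The covariance comes from a subject effect: "A random effect for subject will be fitted to account for covariance among repeated measures on the same individuals". The overall treatment effect is a separate linear contrast, the "between-group difference in change from baseline (change from T1 averaged over T2 to T4").

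**Aim (section 3, Assessments).** "The study aim is to test whether the BA/PS intervention affects the" slope of recovery, which agrees with a focus on trajectories.

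**Assurance (section 9, Adjustment for Multiple Inference).** FDR is set at 10%, and the text concludes: "As shown above, the sample is well powered to detect relevant effect sizes on the primary outcomes, even after multiplicity adjustment". The only calculation to which this can refer is the time-averaged one.

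**The concern.** Three quantities are in play: the averaged post-baseline difference (sized), the interaction (the focus of inference) and the averaged change from T1 (the reported overall effect). They have different variances, and the first two have different degrees of freedom. The Modeling text does not say how T1 means are parameterised. The change-from-T1 wording suggests that they are free in each arm, which is an inference. On that reading, the interaction and the change contrast are hardest to power at low within-subject correlation, whereas the sized test is hardest to power at high correlation. The stated range therefore bounds neither of them.

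A null interaction result would then be read against a power assurance that was not calculated for it. The number of tests in the primary FDR family is also not listed. The power paragraph divides by three, while section 2 calls one outcome primary and the others secondary.

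**Working it through.** **Inputs.** From section 9: δ = 3.94, SD = 10, α = .05/3, 80% power, ρ from 0.2 to 0.8, 120 completers per arm, FDR 10%. From section 3: four assessments, so a categorical interaction with two arms has (4−1)(2−1) = 3 df. Assumed: two-sided tests; compound symmetry, which a random subject intercept implies; and a constant difference of 3.94 at T2 to T4 unless stated.

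**1. Reproduce the protocol's figure.** For 1-df tests, n = 2(z₁₋α/₂ + z₀.₈)² · SD² · f / δ². Here (z₁₋α/₂ + z₀.₈)² = 10.469, so n = 2 × 10.469 × 100 / 15.52 × f = 134.88 f. For the mean of three post-baseline scores, f = (1 + 2ρ)/3:
- ρ = 0.2: 134.88 × 0.4667 = 62.9, stated as 63
- ρ = 0.8: 134.88 × 0.8667 = 116.9, stated as 117

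The arithmetic is right, and it is a 1-df test that does not use T1.

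**2. Change-from-T1 contrast, T1 free.** f = 4(1−ρ)/3 gives 143.9 at ρ = 0.2, 89.9 at 0.5 and 36.0 at 0.8.

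**3. 3-df interaction, T1 free.** The arm differences in change have covariance proportional to SD²(1−ρ)(I + J). For a constant δ the noncentrality is λ = 0.375 n δ² / [SD²(1−ρ)]. At .05/3, 80% power needs λ = 14.05. At ρ = 0.2, n = 14.05 × 0.8 × 100 / (0.375 × 15.52) = 193.1.

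**4. Same 3-df test, T1 means constrained equal.** Conditional on T1, the T2 to T4 covariance is SD²(1−ρ)(I + ρJ), so λ = 3nδ² / [2 SD²(1−ρ)(1+3ρ)]. At ρ = 0.2, n = 77.2.

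Required n per arm for 80% power, and power with 120 per arm, at α = .05/3:

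| ρ | Sized test, n | Change contrast, n | 3-df free T1, n | 3-df free T1, power | 3-df constrained T1, n | 3-df constrained T1, power |
|---|---|---|---|---|---|---|
| 0.2 | 62.9 | 143.9 | 193.1 | 53.5% | 77.2 | 95.8% |
| 0.4 | 80.9 | 107.9 | 144.8 | 69.9% | 79.6 | 95.2% |
| 0.5 | 89.9 | 89.9 | 120.7 | 79.7% | 75.4 | 96.3% |
| 0.8 | 116.9 | 36.0 | 48.3 | 99.8% | 41.0 | >99% |

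The constrained test is weakest near ρ = 0.33 (n = 80.4; power 95.0%). A 4,000-trial simulation of the free-T1 F test gave 53.5% at ρ = 0.2 and 78.2% at 0.5. The change contrast has 71% power at ρ = 0.2.

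**5. Under the planned FDR rule.** This step simulates Benjamini-Hochberg at 10%, with an assumed family of three and cross-outcome correlation 0 to 0.6. Power is for satisfaction with the free-T1 3-df test at ρ = 0.2. The 143 per arm is an approximate effective size when partial data are used (150 randomised per arm, 20% dropout assumed to be monotone and spread evenly over T2 to T4).

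| Outcomes at their minimally important difference | 120/arm | 143/arm |
|---|---|---|
| All three | 77–78% | 84–85% |
| Two PROMIS scales | 71–72% | about 80% |
| Satisfaction only | 65% | 74% |
| All three, family of five (two null productivity outcomes) | 69–70% | 78–79% |

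At ρ = 0.3 with all three benefiting, power is 82–83% and 89–90%. On the same rule at ρ = 0.2 and 120 per arm, the change contrast has 89–90% (all three) or about 81% (satisfaction only). The constrained 3-df test has 99% or 98%.

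**The case against.** The strongest reply is that the shortfall is confined to a corner. The .05/3 level is for planning only. Analysis uses FDR at 10%, and section 9 (Intent to treat) says: "All available data from all participants who undergo randomization will be included in the analyses according to the group assigned". On that footing, with all three outcomes at their minimally important difference, the free-T1 interaction reaches 84–85% even at ρ = 0.2. The 53.5% figure needs low correlation, the Bonferroni level and completers only, all at once. This stands, and it is why underpowering is not claimed.

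The shape of the effect also matters. A rising pattern with the same average (1.97, 3.94, 5.91) raises free-T1 power at ρ = 0.2, .05/3 and 120 per arm from 53.5% to 81.7%. This stands as well; the constant effect is an assumption.

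Next, under randomisation the change contrast estimates the same quantity as the sized test, and under FDR it has 81–90% power at ρ = 0.2. So the assurance is substantively true for what the protocol calls the overall effect, given a constant effect and a family of three. But that contrast is not named as the focus, its variance differs from the one used, and no calculation for it is shown.

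Finally, a free-T1 interaction test is valid, so constraining T1 is a gain in efficiency. That is fair. The error is the mismatch between the power statement and the test; the constraint is the cheapest way to keep the trajectory focus with adequate power.

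**Conclusion.** The concern holds. The 63 to 117 per arm belongs to a 1-df post-baseline average. Neither the 3-df interaction nor the change-from-T1 contrast is sized, and the assurance under Adjustment for Multiple Inference refers back to the wrong test.

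The consequence is conditional. With free T1 means and a constant 3.94, the interaction reaches 80% at ρ of about 0.5 and above, even at .05/3. At ρ near 0.2 the answer turns on the number of outcomes that benefit, the size of the FDR family, the effect pattern and the use of partial data, none of which the power paragraph addresses. These figures rest on compound symmetry, SD 10 and the inferred free-T1 parameterisation. The mismatch itself rests on none of them. It should be fixed before analysis.

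**What to change.** Before inferential analysis:

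1. In the mixed model, constrain T1 means equal across arms, or use T1 as a covariate. Name the 3-df test of the T2 to T4 arm differences as the deciding test for hypothesis 1a. This keeps the focus on trajectories.
2. Report the averaged T2 to T4 arm difference as the effect estimate, with the difference at each visit.
3. Restate power for that test by ρ and effect pattern at the FDR level, list the tests in the primary FDR family, and correct the back-reference in the assurance.

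Making the averaged 1-df test decisive would also align power and analysis, but that is a choice for the team.

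The cost is SAP wording and one recalculated paragraph. The constraint lost no power in any pattern checked. At ρ = 0.2, .05/3 and 120 per arm, an effect at one visit only gives 62% against 53.5% with T1 free, and an effect at two visits gives 90% against 70%. The constraint is valid only if T1 is completed before allocation is known. Section 10 (Internal Data and Safety Monitoring Board) implies that order without stating it, so the SAP should confirm it. Section 10 (Stopping Rules) defers inferential analysis until data collection ends, so the change can still be pre-specified.
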